#### 3.7 Patient Allocation to study groups

There is generally one patient per room and patient assignment to a room is largely driven by unit census (i.e., bed availability) as well as other clinical factors: e.g., need for an isolation room, nursing availability. All of these factors vary independently of the preferences of the patient or research team, reducing the risk for systematic bias. The unit of randomization is by pod on a floor. Research coordinators as part of the "on-boarding process" will also provide culturally competent instructions and in-person teaching for device use.

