#### 3.8 Data collection

This will entail a blend of Epic medical record abstraction and primary data collection using validated surveys. Example of variables to be exstracted from the medical record include patient demographics (e.g., age, sex, race), primary diagnosis (cancer type), body mass index (BMI), timing of AM phlebotomy, comorbid conditions (used to compute Charlson co-morbidity index), length of stay, and 30-day readmission. To reduce survey burden for patients and ensure parity in scope of responses across the 2 groups, the majority of questionnaires will be distributed at two time points - at admission and within 24 hours of the date of discharge. All validated surveys will be administered via the hospital-owned iPad device, via text message or email, or recorded manually. A password-protected database will be used to collate the clinical and outcomes data collected. Lastly, all patients will receive a phone call 24 hours after discharge to ensure all questions are answered and follow-up care has been arranged.

2022-0190 v.23Mar2023 Page **4** of **18** 

The digital device is worn on the wrist, like a watch, and provides continuous vital sign monitoring using a three-lead system that included electrocardiography (ECG), pulse oximetry, continuous noninvasive blood pressure, mean arterial pressure, temperature, respiratory rate, heart rate, and pulse rate. Patients will be able to view their vital signs on the wrist-worn device's display screen.

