#### 3.9 Outcomes

Patient-Centered Outcomes (Primary): The present study will be powered to the EQ-5D measure at discharge, our primary outcome, which allows us to discern variations in self-reported quality-of-life over the course of the inpatient care episode that is attributable to our intervention (Table 2)

Primary Outcome	Instrument	Duration	Analysis level	Assessment Calendar
Quality of Life	EQ-5D-5L	2-5 min	Patient	Admit, discharge +/- 1
				day
Secondary Outcome	Instrument	Duration	Analysis level	Assessment Calendar
Patient Engagement	PAM-13	3 min	Patient	Admit, discharge +/- 1
				day
Patient Mood	Hospital Anxiety &	2-5 min	Patient	Admit, discharge +/- 1
	Depression Survey (HADS)			day

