#### 3.10 Statistical Analysis Plan

Means with standard deviations, frequencies and percentages will be used to convey descriptive statistics. Standard tests of association (chi-squared, t-tests) will be used for comparing characteristics between the control and intervention arm. Inverse probability weighting using propensity scores modeled from baseline covariates and instrumental variable analysis will be the quasi-experimental approach used to minimize any confounding bias from our pseudorandomization process. We will model most outcomes with weighted multivariate generalized mixed effects regression models, focusing primarily on estimate the average treatment effect. The effect of unit will be modeled using a random intercept term. Care utilization outcomes will be compared using standard time-to-event models and log-rank testing. Final analyses will be performed when all data has been entered, cleaned, and locked.

All analyses will be based on an intent-to-treat framework. For missing covariate values, a multiple imputation approach will be used. Outcomes will be assumed to be missing at random; a sensitivity analysis will be conducted to assess the robustness of significant findings to different magnitudes of missing data mechanisms.

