#### 3.11 Sample size justification

Preliminary calculations, based on an estimated conservative change of 10% from baselines scores in QOL, as measured by the EQ-5D instrument total score (with a baseline of mean of 13 units and standard deviation of 5 units). We expect to detect a significant change with at least 80% power using 250 patients per treatment arm. To account for increased estimation variance due to propensity score-based reweighting (and a small rate of drop-out after enrollment), we plan to enroll 350 patients per treatment arm to ensure a reasonable expectation of significance.

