#### 4.4 Study Methods

- a. Study design: The pilot sub-study will be integrated into the parent trial. This pilot study leverages a twogroup, pre-post test design to conduct preliminary tests for differences between the experimental arm (PROSPER intervention with digital vital sign monitoring) and the control arm (PROSPER intervention without digital vital sign monitoring) on objective sleep parameters and patient reported sleep disturbances and fatigue.
- b. Recruitment: Once participants are enrolled in the parent trial, they will be evaluated for inclusion in the pilot sub-study based on the availability of the device that measures objective sleep parameters (Actiwatch Spectrum Pro®). Thirty wrist actigraphy devices (Actiwatch Spectrum Pro®) are available for use at any given time. Fifty participants from the patient care units designated as the intervention arm for the parent trial will be enrolled as treatment patients in the substudy; fifty participants from the patient care units designated as the control arm will be enrolled as control patients in the substudy. Participants will be consecutively enrolled in the sub-study as they are enrolled in the parent study although enrollment may pause if wrist actigraphy devices are not available.
- c. Instrumentation: Objective sleep parameters will be assessed with the Actiwatch Spectrum Pro® during the course of hospitalization, consistent with the parent trial. Patient-reported sleep disturbances will be measured with the PROMIS Sleep Disturbance Adult Short Form. Patient-reported fatigue will be measured in real-time with a one-time global fatigue intensity rating over the course of the hospitalization and the PROMIS Fatigue Adult Short Form. The PROMIS instruments will be completed upon enrollment and discharge +/- 1 day, consistent with the parent trial.

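### PROMIS is to be compared by t-tests although enrolment scores are collected; secondarily, the primary EQ-5D analysis does not name the admission score

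*Combined protocol and SAP*

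**What the plan says.** **Sub-study.** Section 4.4 (Study Methods, item a) describes a two-group "pre-post test design to conduct preliminary tests for differences between the experimental arm" and the control arm. Section 4.4 (Data Collection) has both PROMIS forms completed at enrolment and again within a day of discharge. Section 4.5b then compares the arms on these scores by two-sided independent-samples t-tests. It does not say whether the discharge score or the change from enrolment is tested. ANCOVA with baseline measures appears only in Section 4.5a, as an exploratory step for the actigraphy outcomes.

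**Parent trial.** Section 3.9 states "The present study will be powered to the EQ-5D measure at discharge, our primary outcome", and Table 2 schedules EQ-5D-5L at admission and discharge. Section 3.8 confirms that "the majority of questionnaires will be distributed at two time points - at admission and within 24 hours of the date of discharge". Section 3.10 relies on "Inverse probability weighting using propensity scores modeled from baseline covariates and instrumental variable analysis" to limit confounding. Of the outcome analysis it says "We will model most outcomes with weighted multivariate generalized mixed effects regression models, focusing primarily on estimate the average treatment effect", with a random intercept for unit. It adds "For missing covariate values, a multiple imputation approach will be used". It lists no covariates for either the propensity score or the outcome model.

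**The concern.** An enrolment score of the same instrument is usually a good predictor of the discharge score. A t-test on discharge scores makes no use of it. A t-test on change scores uses it with a fixed coefficient of 1, which is inefficient unless the correlation is close to 1. The PROMIS comparison is therefore less precise than the collected data allow, and the choice between the two t-tests is left open.

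In the parent trial the question is what has been left unsaid. Allocation follows bed availability "as well as other clinical factors: e.g., need for an isolation room, nursing availability" (Section 3.7), so the arms could differ at admission, and Section 3.10 itself expects some confounding. The admission value of the primary outcome is the obvious variable to name. Because it is not named, the text permits three primary analyses: admission EQ-5D in neither the weights nor the model, in the weights only, or in both. In an unblinded study that choice is better fixed before the data are seen.

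**Working it through.** **Inputs from the documents.** Sub-study: 50 per arm (Section 4.3); PROMIS SD 10, which is the reference-population value (Section 4.4, item f). Parent trial: EQ-5D "with a baseline of mean of 13 units and standard deviation of 5 units", a 10% change and 250 per arm (Section 3.11), so the target difference is 0.10 × 13 = 1.3 points.

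**Assumptions.** Two-sided alpha 0.05, which is not stated for the parent trial. Correlations r between first and discharge score of 0.3, 0.5 and 0.7; the documents give none.

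**1. PROMIS precision.** The documents give no figure to reproduce. The 95% CI half-widths for the difference between arms are:

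- t-test, discharge score: t(98) × SD × √(2/50)
- t-test, change score: t(98) × SD × √(2(1−r)) × √(2/50)
- ANCOVA: t(97) × SD × √(1−r²) × √(2/50)

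Here t(97) and t(98) are both about 1.98, and √(2/50) = 0.2.

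| r | Discharge t-test | Change t-test | ANCOVA |
|---|---|---|---|
| 0.3 | 3.97 | 4.70 | 3.79 |
| 0.5 | 3.97 | 3.97 | 3.44 |
| 0.7 | 3.97 | 3.07 | 2.83 |

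Against discharge scores the reduction is 1 − √(1−r²), or 5/13/29%. Against change scores it is 1 − √((1+r)/2), or 19/13/8%. At r = 0.5, letting the SD run from 8 to 12 gives 2.75 to 4.13 by ANCOVA, against 3.18 to 4.76 for either t-test. The formula leaves out the small loss from chance imbalance in the enrolment score.

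**2. The plan's own power.** SE = 5 × √(2/250) = 0.447 and 1.3/0.447 = 2.91, which gives 82.7% by the t-test calculation. This meets the stated minimum of 80%. It uses the full SD of 5, so it takes no credit for baseline adjustment.

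**3. Admission EQ-5D against no adjustment.** Residual SD = 5√(1−r²) = 4.77/4.33/3.57, so power at 250 per arm is 86.0/91.8/98.2%.

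**4. Admission EQ-5D already in the weights.** Simulation with 250 per arm, no unit effect, a logistic propensity score on admission EQ-5D alone, and 8,000 replicates (4,000 under the null):

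| | Weights only | Weights plus covariate |
|---|---|---|
| True sampling SD | 0.42/0.39/0.32 | 0.42/0.39/0.32 |
| Mean reported SE, weights treated as known | 0.45/0.45/0.45 | 0.43/0.39/0.32 |
| Power | 84/86/91% | 86/92/98% |
| Rejection under the null | 4.2/2.3/0.5% | 5.1/5.0/4.8% |

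The true precision is the same; only the reported SE differs. With weights only and an SE that accounts for the estimated propensity score (1,500 replicates), the mean SE is 0.425/0.386/0.319 and power is 85/91/98%.

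**5. Admission EQ-5D in neither place.** With equal SDs, a true difference D between the arms at admission shifts the discharge difference by r × D. For an assumed D of 0.5 point the shift is 0.15/0.25/0.35, or 12/19/27% of 1.3. For D of 1.0 it is 0.30/0.50/0.70, or 23/38/54%.

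**6. Units.** Assume two units per arm and 125 patients per unit, with between-unit SD τ treated as known, so SE = √(τ² + 25(1−r²)/125). Going from no adjustment to r = 0.5 raises power from 71.8% to 80.5% at τ = 0.25, and from 49.1% to 53.8% at τ = 0.5. With 2 degrees of freedom instead, the same SEs give 30.6% to 35.5% and 20.9% to 22.7%.

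**The case against.** **Adjustment in the parent trial is largely planned.** Section 3.10 commits to weighting on baseline covariates, to a multivariate outcome model and to imputation of missing covariates. Section 3.9 speaks of variation over the stay, and Section 3.11 sizes the trial on a change from baseline. A reader might infer that the primary analysis ignores admission EQ-5D and is therefore biased. The documents do not support that: the score is unnamed, not excluded. Bias needs both the least natural reading (step 5) and a true difference between the arms at admission. The documents give no figure for such a difference, and Section 3.7 says the allocation factors are independent of patient and team preferences. This objection stands, and it limits the parent-trial point to a request for specification.

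**The power gap with weights only reflects the choice of SE.** This also stands. Section 3.10 names no SE, and one that accounts for the estimated propensity score closes nearly all of the gap without the covariate.

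**The sub-study is a pilot.** Section 4.5b calls the analysis preliminary, and Section 4.1 expects only trends. At r = 0.3 ANCOVA gains just 0.18 point over discharge scores. That limits the importance of the change, not its direction: at every correlation tried, ANCOVA is narrower than either t-test.

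**The baseline may not be clean.** Section 3.5 allows the approach to patients within 1–2 days of admission, and no section says that the admission EQ-5D precedes device placement. Adjusting for a score taken afterwards could remove part of the effect. This is a fair condition on the fix. The same question arises for enrolment PROMIS, because sub-study enrolment follows parent-trial enrolment.

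**Conclusion.** The PROMIS point holds as a free improvement. At 50 per arm and SD 10, ANCOVA shortens the half-width to 3.79/3.44/2.83, from 3.97 (discharge) or 4.70/3.97/3.07 (change), for assumed correlations of 0.3/0.5/0.7. It is a gain in precision in a pilot and no more. It does not extend to the real-time fatigue ratings, which are repeated through the stay and are not an enrolment and discharge pair.

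The EQ-5D point holds as a secondary one: the plan should name a covariate that it already collects. The rise in power from 83% to 86/92/98% is relative to a fully unadjusted analysis with independent patients, which is not what Section 3.10 describes. If the score is already in the weights, the covariate mainly corrects an SE that treats the weights as known.

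A reader might also infer that 250 or 350 per arm is the wrong number. That does not follow, since the stated power is reproduced without any adjustment. Nor does the covariate resolve inference with four units, where between-unit variation could dominate (step 6).

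**What to change.** 1. In Section 4.5b, replace the t-tests for PROMIS Fatigue and PROMIS Sleep Disturbance with ANCOVA of the discharge score on arm and enrolment score, reporting the adjusted difference with its 95% CI. Leave the real-time fatigue analysis as it is.
2. In Section 3.10, state that admission EQ-5D enters the propensity score and is also a fixed effect in the primary model of discharge EQ-5D. Keep the planned weights and the random unit intercept.
3. State that the admission EQ-5D used for this must be obtained before device placement, and check the same for enrolment PROMIS.

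Items 1 and 2 change SAP wording only, since both baseline scores are already collected and no visit is added. Item 3 needs the timing of the questionnaire relative to device placement to be confirmed and recorded. Inference with four units needs separate treatment.

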#### 3.4 Study Design

This is a pragmatic, quasi-experimental study wherein patients admitted for any of the aforementioned conditions will be allocated into treatment (ViSi mobile plus PROSPER) and control (PROSPER only) based on non-critical care bed availability on a floor unit. Specifically, for patients on colorectal service admitted to P10 floor, one side ("unit A") will be designated as an intervention arm while the other ("unit B") will serve as a control arm. For patients admitted to Hospitalist Medicine service; patients on " unit G21" will be designated as the intervention arm, and patients admitted to "unit G22" as the control arm. Our pseudorandomization scheme is based on the naturally occurring random variation in bed assignment by availability across both the intervention and control units on a given floor, or floors at the time of patient enrollment. Since bed designation is made by hospital admissions based on availability, it is independent of the care delivery processes across the study floors / units. Our approach is intended to reduce the

burden on frontline staff, i.e., changing existing workflows to randomize patients and track allocation in a database. It also serves to reinforce the embedded intent of our QI work. Participants, family members and clinicians will not be blinded to the intervention, and given our pragmatic design, we will not attempt to control patients' communication or information-seeking behaviors beyond the pseudo-randomization described above. The intervention wing will employ the following initiatives to improve the sleep quality, level of engagement, and overall care journey of patients.

1. Passive digital monitoring of vital signs – Blood pressure, heart rate, respiratory rate, oxygen saturation, and temperature – will be wirelessly and passively collected using a U.S. Food and Drug Administration-approved wireless technology, which is worn on the wrist and chest (ViSiMobile, Sotera, San Diego, Calif), and recorded data will be sent directly to the electronic medical record (Epic Systems Corporation, Verona,Wis) at protocolized set intervals. Abnormal vitals will trigger a nursing alert via text message or page. If an in-person assessment is warranted, handheld red-spectrum lighting will be used by nursing staff as an alternative to the standard overhead white lighting.

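### The log-rank comparison of length of stay and readmission names no service stratum, although the arms are formed inside two services, and the plan leaves open whether weighting covers it

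*Combined protocol and SAP*

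**What the plan says.** Section 3.4 (Study Design) assigns one intervention unit and one control unit to each service. Colorectal patients on P10 go to unit A (intervention) or unit B (control). Hospitalist patients go to G21 (intervention) or G22 (control). Section 3.7 says "patient assignment to a room is largely driven by unit census (i.e., bed availability) as well as other clinical factors". The only enrolment target is in section 3.11: "we plan to enroll 350 patients per treatment arm to ensure a reasonable expectation of significance". No section sets a target, quota or reporting split by service.

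Section 3.10 first names inverse probability weighting and instrumental-variable analysis as the general approach to confounding from the allocation. It continues "We will model most outcomes with weighted multivariate generalized mixed effects regression models", followed by "The effect of unit will be modeled using a random intercept term". A separate sentence covers length of stay and readmission: "Care utilization outcomes will be compared using standard time-to-event models and log-rank testing". That sentence mentions no stratum, covariate or weight. Service is not named as a covariate anywhere. The examples of record variables in section 3.8 include age, cancer type and comorbidity, but not service.

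**The concern.** The comparison is naturally a within-service one, yet the stated log-rank pools the services. The service mix of each arm depends on the capacity and enrolment of four units. If the intervention arm took a larger share of the shorter-stay service, the pooled test would credit part of the service difference to the device. With the opposite mix, a real benefit could be missed. The unit random intercept belongs to the mixed models and does not enter a log-rank test.

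Reduced length of stay and lower readmission come first in the Hypothesis section, and acute care utilization is secondary objective (a) in section 1.2.

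**Working it through.** **The plan's own figure.** The parent trial's only power statement concerns EQ-5D: difference 0.10 × 13 = 1.3, SD 5, 250 per arm. With two-sided alpha 0.05 (assumed), 1.3 / (5 × √(2/250)) = 2.907, and Φ(2.907 − 1.960) = 82.8%. The stated 80% or more is met (233 per arm would be enough). No power is given for length of stay, so this figure does not bear on the point.

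**Inputs from the documents.** 350 per arm (3.11); stays of at least 3 nights (3.2); two services with one unit per arm in each (3.4).

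**Assumptions.** The documents give no service-specific stays, bed counts or mix. Stays are taken as lognormal, conditional on exceeding 3 days, with no censoring and no treatment effect. Medians before the cut are 4 and 5.6 days. Mix is the share of the shorter-stay service, intervention versus control.

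**Type I error, nominal 5%, 10,000 simulated trials per setting, no unit effects:**

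| Mix | Unstratified, log-SD 0.5 | Unstratified, log-SD 0.8 |
|---|---|---|
| 50 vs 50 | 4.6% | 4.9% |
| 52.5 vs 47.5 | 5.9% | 5.2% |
| 55 vs 45 | 8.9% | 6.6% |
| 60 vs 40 | 23.3% | 11.1% |

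Stratified by service, the error is 4.9–5.5% throughout. Repeat runs move the unstratified figures by about a point, hence the rounded ranges of 7–10% and 11–23%.

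- Smaller gap (medians 4 and 4.8 days): 5.5–6.1% at 55/45 and 6.8–10.7% at 60/40.
- Exponential stays, discharge-rate ratios 1.25, 1.5 and 2.0: 6.2, 7.1 and 11.1% at 55/45; 8.3, 16.5 and 37.8% at 60/40. Stratified: 4.5–5.9%.
- Direction (log-SD 0.5): 8.5 of the 8.9% and 23.2 of the 23.3% favour the arm with more short-stay patients.

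**Hidden effect.** With stay beyond 3 days cut by 20% (log-SD 0.5), unstratified power is 89% at equal mix, 73% at 45 vs 55 and 48% at 40 vs 60. Stratified power is 90–91%.

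**Readmission.** Assume 10% and 20% by service. At 55/45 the expected rates are 0.55 × 10 + 0.45 × 20 = 14.5% and 15.5%. The SE is √((0.145 × 0.855 + 0.155 × 0.845)/350) = 0.0270, so the shift is 0.37 SE and the error is 6.6%. At 60/40 (14% vs 16%) it is 11.5%.

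**How a mix difference could arise.** Assume enrolment proportional to beds.

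- 24 vs 16 beds in one service and 20 vs 20 in the other: 24/44 − 16/36 = 54.5% − 44.4%, about 10 points.
- 22 vs 18 in one and 20 vs 20 in the other: 22/42 − 18/38, about 5 points.
- 20 points needs 24/16 in opposite directions in both services: 24/40 − 16/40.
- By chance alone the SD is √(2 × 0.25/350) = 3.8 points. A 10-point difference then occurs in 0.8% of trials, and overall error stays at 5.0%.

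**Weighting instead of stratifying** (robust variance). Weights on service give 4.5–5.8%. Weights on a proxy that matches service in 75% of patients give 7.3% at 55/45 and 15.5% at 60/40. With a 90% match they give 5.2% and 7.2% (log-SD 0.5, wider gap).

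**Unit effects.** With an assumed ICC of 0.01 on log stay across four units, the stratified log-rank error is roughly 11–16%.

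**The case against.** The strongest reply is that the weighting sentence in section 3.10 comes before every model and is not limited to any outcome. Service mix is exactly the kind of confounding it targets, and the phrase about most outcomes describes a model form rather than an exemption. This stands as a possible reading. A reader might infer that the log-rank is definitely unweighted, and the text does not establish that. It also does not say that the weights apply, or that service is in the propensity model.

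Service need not be named if other covariates track it closely, and cancer type, age and comorbidity may do so. The 90% proxy result supports this and the 75% result does not. The documents do not show how close the match is. The time-to-event models could also carry covariates, and the planned comparison of characteristics by arm could reveal an imbalance if service is tabulated. Neither is stated.

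The imbalance is wholly assumed. Section 3.4 argues that bed assignment is independent of care processes, and chance imbalance does no harm overall. The 23% figure needs a 20-point difference, the wider gap and the smaller SD together.

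Finally, at ICC 0.01 clustering alone can inflate the error more than a 10-point mix difference does, and stratification leaves it in place. That is correct, and it limits what the fix achieves.

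**Conclusion.** The point holds as a conditional one. The arms are formed inside two services and only the total per arm is fixed. Section 3.10 does not specify how the care utilization comparison accounts for service. If mix differs systematically, the service gap is the wider one assumed, and neither strata nor effective weights are applied, type I error is about 7–10% at a 10-point difference and 11–23% at 20 points. At equal mix or with chance imbalance only, it is about 5%. The outcomes are secondary, but the error is directional and can be removed by wording, so the change should be made.

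Three stronger readings are not supported:

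- *The arms are unbalanced by service.* The documents give no bed counts, enrolment or stays by service.
- *Stratifying makes the log-rank valid.* It restores about 5% only without unit effects.
- *Leaving service out makes the primary mixed model conservative.* The documents give neither an EQ-5D gap between services nor an ICC. At an assumed ICC of 0.01 with a z test, error runs from 12% with no gap to 0.4% with a 2-point gap, so no direction follows. The primary model and inference from four units are a separate matter.

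**What to change.** In section 3.10:

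1. Stratify the log-rank test and the time-to-event models by service (colorectal, hospitalist). Service is the right stratum: each unit belongs to one arm, so strata by unit would contain no comparison.
2. Name service as a covariate in the propensity model.
3. State that the inverse probability weights apply to the care utilization outcomes, and name the variance estimator used with them.
4. Report enrolment by unit and service, so that readers can see the mix.
5. State that the stratified test does not account for clustering in four units and that its error may exceed 5% for that reason.

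The cost is SAP wording and one variable known for every patient from the admitting unit. Stratifying loses no power at equal mix: 90.8% versus 89.4% unstratified at log-SD 0.5, and 72.7% versus 71.8% at log-SD 0.8. The downside is that the stratified analysis assumes a common hazard ratio in the two services. Any service-specific effects should be descriptive, because each compares one unit with one unit.

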#### 1.2 Secondary Objectives:

- a. Assess the impact of our sleep enhancement intervention on acute care utilization e.g. length of stay, 30-day readmissions
- b. Assess the implementation and feasibility of wearable digital vital signs capture in an inpatient oncologic setting using validated instruments such as system usability scale (SUS) and Weiner implementation outcomes (AIM, FIM, IAM).
- c. Assess the impact, via validated survey instruments, of our sleep enhancement intervention on patient mood, patient activation and satisfaction with inpatient stay experience.

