#### Additional Outcomes:

- a. Acute care utilization: Median length of stay (LOS) in hours, all-cause Emergency Room (ER) visit, and hospital readmission within 30 days postoperatively
- b. Implementation and feasibility outcomes: We will also perform psychometric assessments, from the perspective of patient and nursing stakeholders, of the implementation process and perceived effectiveness associated with our passive vital sign monitoring intervention. Three 5-item validated implementation metrics of Acceptability (AIM), Appropriateness (IAM), Feasibility (FIM) will be used to monitor and evaluate the adoption of our passive vital signs monitoring intervention. We will also leverage the system usability scale (SUS) to examine the usability and ergonomics of the passive vital sign monitoring platform (Table 3).

Outcome	Instrument	Duration	Analysis level	Assessment Calendar
Intervention	System Usability Scale	5 mins	Patient, Nurse	Admit, discharge +/- 1
usability				day
Intervention	Acceptability of Intervention	3 min	Patient, Nurse	Admit, discharge +/- 1
acceptance	measure (AIM)			day
Intervention	Feasibility of Intervention	2-5 min	Patient, Nurse	Admit, discharge +/- 1
feasibility	Measure (FIM)			day
Intervention	Intervention Appropriateness	2-5 min	Provider,	Admit, discharge +/- 1
appropriateness	Measure (IAM)		Nurse	day

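### The log-rank test named for length of stay, ER visits and readmission cannot allow for unit, although treatment is assigned by whole unit; the resulting false-positive inflation can be large for length of stay and is milder for readmission

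*Combined protocol and SAP*

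**What the plan says.** Section 3.10 first deals with the bulk of the outcomes: "We will model most outcomes with weighted multivariate generalized mixed effects regression models". It then states "The effect of unit will be modeled using a random intercept term". The next sentence gives acute care utilization its own method: "Care utilization outcomes will be compared using standard time-to-event models and log-rank testing". No frailty term, cluster-robust variance, stratification or weighting is stated for these outcomes.

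The outcomes concerned are listed under Additional Outcomes in section 3.9: "Median length of stay (LOS) in hours, all-cause Emergency Room (ER) visit, and hospital readmission within 30 days postoperatively". The first secondary objective in section 1.2 reads "Assess the impact of our sleep enhancement intervention on acute care utilization e.g. length of stay, 30-day readmissions".

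On allocation, section 3.7 says "The unit of randomization is by pod on a floor". Section 3.4 makes one side of the colorectal floor (P10 unit A) the intervention side and the other (unit B) the control side. For the hospitalist service, G21 is intervention and G22 is control. That is four units in all, two per arm, and within each service arm and unit are the same thing.

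**The concern.** A log-rank test takes its variance from patients treated as independent. Here a patient's arm is decided by the unit the patient lies on. If two wards discharge, follow up or readmit at different rates for any reason other than the device, that difference goes straight into the arm comparison and the log-rank variance makes no allowance for it. By modelling unit for its other outcomes, the plan accepts that units may differ.

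Shorter stay and fewer readmissions are both named in the study hypothesis. As written, an ordinary difference in discharge speed between two pairs of wards could be reported as a significant effect of the monitor.

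**Working it through.** **The plan's own figure.** No power, alpha or ICC is given for utilization. The only parent-trial calculation is for EQ-5D (section 3.11): a change of 10% of 13, that is 1.3 units, with SD 5. At two-sided 5% (assumed), n = 2 × (1.960 + 0.842)² × (5/1.3)², or 233 per arm. With 250 per arm, 1.3 / (5 × √(2/250)) = 2.907 and power is Φ(2.907 − 1.960) = 82.8%. The statement of at least 80% is therefore correct. The step from 250 to 350 is attributed to reweighting and drop-out, and unit clustering is not mentioned.

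**Inputs.** From the documents: 350 enrolled per arm (3.11) and two units per arm (3.4). Assumed: an equal split, so m = 175 per unit; two-sided 5%; no device effect; all patients discharged alive, so 700 discharge events; and 20% readmission, so 0.20 × 700 = 140 events. The 20% borrows the Medicare background figure in section 2.0.

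**Length of stay, ICC scale.** Design effect DE = 1 + (m − 1) × ICC. The true error of a nominal 5% test that omits unit is 2 × [1 − Φ(1.96/√DE)]. Log-rank simulations used four units of 175, log length of stay with a unit effect, and no censoring.

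| ICC | DE | Formula | Simulated log-rank |
|---|---|---|---|
| 0.001 | 1.17 | 7.1% | about 6% |
| 0.005 | 1.87 | 15.2% | 13% |
| 0.01 | 2.74 | 23.6% | 20-21% |
| 0.02 | 4.48 | 35.4% | 32% |
| 0.05 | 9.70 | 52.9% | 48-49% |

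At ICC 0 the simulated rate is 4.6%, so the excess comes from the unit effect. With 125 per unit the formula gives 12.4% at ICC 0.005 and 19.0% at 0.01. For scale, ICC 0.01 is a unit SD of √0.01, one tenth of the total SD of log length of stay.

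**Both outcomes, log-hazard scale.** Let s be the SD of the unit log hazard. The log-rank variance of the log hazard ratio is about 4/events. Each arm averages two units, so unit variation adds s²/2 + s²/2 = s². The true error is 2 × [1 − Φ(1.96 × √((4/events) / (4/events + s²)))].

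| s | Length of stay, 700 events: formula (simulated) | Readmission, 140 events: formula (simulated) |
|---|---|---|
| 0.05 | 10.2% (9.7%) | 6.0% (6.8%) |
| 0.10 | 23.7% (22.4%) | 9.2% (10.3%) |
| 0.20 | 48.8% (48.8%) | 20.6% (21.8%) |

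With 10% readmission (70 events) the formula gives 5.5%, 7.1% and 13.3%. Inflation is milder for readmission because 4/140 = 0.0286 is five times 4/700 = 0.0057, so the same s² adds proportionately less.

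**Stratifying by service.** Within a service the comparison is one unit against one unit, with unit variance 2s². Averaging two services gives (2s² + 2s²)/4 = s², the same as before. The simulation agrees: for length of stay at s = 0.10 the rate is 22.4% unstratified and 23.3% stratified.

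**The case against.** - **The random-intercept sentence stands on its own.** It could be meant for every model, and a Cox model with a shared frailty might still be called standard. This stands for the models: a reader might infer that the plan ignores unit in all its time-to-event work, but the text shows only that their handling of unit is unstated. It does not rescue the log-rank test, which has no place for a random intercept.
- **Beds are filled by availability (3.4, 3.7).** This bears on which patients reach which unit. It does not make the units discharge or follow up at the same rate. Propensity weights balance patient covariates and cannot remove a ward effect either.
- **No ICC is given.** The relevant variation is between units within one service, and for colorectal these are two sides of one floor, so it may be small. This stands. At ICC 0.001 the error is only 6-7%.
- **Readmission behaves differently.** A reader might carry the length-of-stay percentages over to every utilization outcome. The event counts do not support that.
- **These are secondary outcomes.** EQ-5D is the primary and the only powered outcome, and no confirmatory alpha is attached to utilization. This stands and limits the weight of the point.
- **The contrast with the other outcomes can mislead.** A reader might infer that outcomes with a unit random intercept are adequately protected. Four units less two arm means leave about 2 degrees of freedom between units, where the t critical value is 4.30 rather than 1.96. The mixed models meet the same limit.

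**Conclusion.** The point holds for the log-rank test on any reading of section 3.10: the named test omits between-unit variance that the allocation puts into the arm comparison, and a service stratum does not repair it. For length of stay, modest unit variation is enough to matter, with error near 20-24% at ICC 0.01 or at a unit log-hazard SD of 0.10. For readmission the direction is the same but the size is moderate, about 6-9% at SD 0.05 to 0.10 and 21% at 0.20. ER visits were not calculated separately.

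The sizes rest on assumed unit variation, an equal split of patients over units, a two-sided 5% level and the assumed readmission rate. The documents do not support saying that every utilization p-value is far too small under slight variation, or that the time-to-event models are known to omit unit. The plan should be corrected here, but the primary analysis does not turn on it.

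**What to change.** In section 3.10:

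1. State that the ordinary log-rank p-value will not be used as evidence of a device effect on length of stay, ER visit or readmission.
2. Report a service-stratified Cox hazard ratio using the plan's propensity weights. Recompute its interval as log HR ± 1.96 × √(SE² + s²), over a range of s fixed in advance for each outcome on the log-hazard scale, for example 0.05 to 0.20. If unit sizes are unequal, multiply s² by the sum of the squared unit shares over both arms, which equals 1 for an equal split. Fix s rather than estimate it, because four units cannot estimate a frailty variance reliably.
3. Report the value of s at which significance is lost: s* = √((log HR/1.96)² − SE²).
4. Label utilization p-values exploratory, and say that a difference may reflect the units rather than the device.
5. Note that the four-unit limit also applies to the mixed models for the other outcomes.

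A pass/fail rule tied to one assumed ICC is not needed. At ICC 0.05 it would require a hazard ratio of exp(1.96 × √(9.70 × 4/700)) = 1.59 for discharge or exp(−1.96 × √(9.70 × 4/140)) = 0.36 for readmission, on the strength of a number the documents do not contain.

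The cost is SAP wording, a little more analysis and wider intervals, with no extra patients or data. Before any loss from weighting, the smallest significant hazard ratio for discharge is exp(1.96 × √(4/700)) = 1.16 with no unit variation and exp(1.96 × √(4/700 + 0.01)) = 1.28 at s = 0.10. For readmission it moves from exp(−1.96 × √(4/140)) = 0.72 to exp(−1.96 × √(4/140 + 0.01)) = 0.68.
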